	
safety review team approval of whether the participant can still be vaccinated, although cases should still be notified to the sponsor.
 
Added that in case of out of window study vaccinations there should be an interval of at least 28 days between subsequent study vaccinations.
	
12.3.3 Pregnancy	Clarified that any postnatal sequelae in an infant will be collected if possible.	Clarification upon ethics committee request.
1.1.2 Background on the Study Vaccines REFERENCES	The background section of the protocol has been updated with a summary of the HPX2008/HVTN 705 results.	Update
TIME AND EVENTS SCHEDULE 9.1.5 Post-vaccination Follow-up Phase 10.2 Discontinuation of Study Vaccination/Withdrawal from the Study	Specified that participants who received the first 3 vaccinations but discontinue study vaccination before receiving the 4 th vaccination, should continue with safety, immunogenicity and HIV diagnosis assessments as planned. All other participants who discontinue study vaccination, should continue with safety and HIV diagnosis assessments as planned.	To minimize blood draws and testing for participants not contributing to the per-protocol population to be used for the primary efficacy analysis.
4.3 Prohibitions and Restrictions	Clarified that for surgeries mentioned in exclusion criterion 3, it will be per investigator's judgement whether the surgery would interfere with protocol assessments during the study. The safety review team will be available for consultation, where appropriate.	Clarification

Amendment 5 (19 May 2021)

Overall Rationale for the Amendment: This amendment has been created to provide information and guidance for investigators on signs and symptoms and on medical management should very rare events of thrombosis with thrombocytopenia syndrome (TTS) occur, as observed in another Ad26-based vaccine program (Ad26.COV2.S, COVID-19 vaccine). The Ad26.Mos4.HIV vaccine uses the same Ad26 vector as Ad26.COV2.S, but has different transgene inserts. To date, no cases of TTS have been reported in Janssen's Ad26.Mos4.HIV clinical studies nor in any other Ad26-based non-COVID-19 vaccine programs from Janssen. Nonetheless, TTS will be followed in this protocol as adverse event of special interest (AESI) that needs to be reported to the sponsor within 24 hours of awareness. Additional changes are listed below.

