- q Participants who have been prematurely withdrawn from study vaccine administration will be encouraged to complete the visit schedule as planned with assessments per the [Time and Event Schedule](#), including assessments of safety and HIV diagnosis. Participants who received the first 3 vaccinations but discontinue study vaccination before receiving the 4th vaccination, should continue the visit schedule as planned with assessments per the Time and Event Schedule including assessments of safety, immunogenicity and HIV diagnosis. They will also be reminded not to have HIV testing outside of the study protocol as this could lead to misdiagnosis and unblinding.
- r Participants will remain under observation at the study site for at least 30 minutes for presence of any acute reactions.
- s All participants will record solicited signs and symptoms in a diary for 7 days post vaccination.
- t Unsolicited adverse events will be recorded for all participants until 28 days after each vaccination.
- u Applicable from the time of local approval of protocol amendment 5 onwards: AESIs (including potential AESIs) are to be reported to the sponsor until 6 months after the last vaccination (see Section [12.3.4](#)). In case of a potential AESI of TTS, a serum sample should be obtained to test for anti PF4 at the local laboratory or substitute local laboratory, if possible; repeat testing may be requested for confirmation upon sponsor discretion. A test for anti PF4 will also be performed on a stored pre vaccination sample, if possible. Serious adverse events, MAAEs, and adverse events leading to discontinuation will be recorded until the participant's last study contact.
- v The site staff and the participant will make multiple efforts in good faith to be in contact after the last day of the reactogenicity period, or sooner if indicated, to discuss presence of any signs and symptoms of reactogenicity. Participants who self report any post vaccination reaction greater than mild are seen by a clinician within 48 hours after onset, unless the reaction is improving and/or has resolved completely.
- w The recall period of the questionnaire is the last month.
- x All participants will be asked about their level of absenteeism at each visit except for Visit 2a, 3a, 4a and 7a. At Visit 8, approximately 1 month post vaccination 4, participants will be asked about the acceptance of the vaccine regimen.

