Visit 9 to 14 are clinic visits that will include a targeted physical examination (full physical examination at Visit 14), recording of serious adverse events, MAAEs and adverse events leading to study discontinuation and HIV reduction counseling as described above for Visit 8. AESIs are to be collected up to Visit 10 (6 months after the last vaccination). Samples for HIV testing will be collected at each visit. The level of absenteeism since their last visit will be recorded. The use of PrEP, PEP, hormonal therapy, hormone-based contraception, and all COVID-19 vaccinations should be recorded at each visit. All other concomitant therapies should also be recorded if administered in conjunction with new or worsening adverse events reported per protocol requirements. Participants will complete a questionnaire on the use of and, if applicable adherence to PrEP and blood for dried blood spots will be collected for participants who have their visit on pre-specified calendar days (may differ per site).

In addition:

- If applicable, unsolicited AEs will be recorded at Visit 8
- A urine pregnancy test should be performed every 3 to 6 months
- Blood samples for syphilis serology determination will be collected and tests for chlamydia/gonorrhea will be performed at Visit 10, 12 and 14.
- Blood samples for humoral (all participants) immunogenicity assays will be collected at Visit 10, 12 and 14.

- A sexual activity questionnaire will be completed at Visit 12.
- A social impact questionnaire will be completed at Visit 14.
- Gender identity will be recorded at Visit 12.

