9.4. Safety Evaluations

Details regarding the independent DSMB are provided in [Section 11.9](#).

Any clinically significant abnormalities that are considered related to vaccination persisting at the end of the study/early withdrawal will be followed by the investigator until resolution or until a clinically stable condition is reached (see Section 12.3.2).

All adverse events and laboratory data will be graded for severity according to the criteria presented in Section 12.1.3.

Adverse Events

All serious adverse events and adverse events and special reporting situations, that are related to study procedures or that are related to non-investigational concomitant sponsor products will be reported from the time a signed and dated ICF is obtained until the end of the study/early withdrawal. Clinically relevant medical events not meeting the above criteria and occurring between signing of ICF and the moment of first vaccination will be collected on the Medical History CRF page as pre-existing conditions.

Solicited adverse events, collected through a diary, will be recorded daily for each vaccination from the moment of vaccination until 7 days post-vaccination.

All other unsolicited adverse events and special reporting situations will be reported for each vaccination from the moment of vaccination until 28 days post-vaccination. Unsolicited adverse events with the onset date outside the timeframe defined above (>28 days after previous study vaccination), which are ongoing on the day of the subsequent vaccination, should be recorded as such.

From the time of local approval of protocol amendment 5 onwards, TTS is considered to be an AESI (see Section 12.3.4). Thrombotic events and/or thrombocytopenia (defined as platelet count below the LLN range for the testing lab) are considered to be potential AESIs. All AESIs, including potential AESIs, will be reported to the sponsor from the moment of first vaccination until 6 months after the last vaccination. Each potential AESI will be reviewed to identify a TTS case.

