11.6. Safety Analysis

No formal statistical testing of safety data is planned. Safety data will be analyzed descriptively. All safety analyses will be tabulated by vaccination group (active vaccine, placebo) and based on the FAS.

Tabulations will be presented by time of occurrence relative to the preceding vaccination (7 days for solicited adverse events and 28 days for unsolicited adverse events, 6 months after last vaccination for AESIs).

Baseline for all safety parameters will be defined as the last evaluation done before the first dose of study vaccine.

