12.3.4. Adverse Events of Special Interest

Adverse Events of Special Interest (AESIs) (including potential AESIs) are significant AEs that are judged to be of special interest because of clinical importance, known or suspected class effects, or based on nonclinical signals. AESIs (including potential AESIs) will be carefully monitored during the study by the sponsor.

AESIs (including potential AESIs) must be reported to the sponsor within 24 hours of awareness irrespective of seriousness (ie, serious and nonserious AEs) or causality following the procedure described above for SAEs.

AESIs (including potential AESIs) must be reported using the AESI checkbox in the eCRF using the eCRF completion guidelines.

Specific requirements for the AESI are described below.

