## 4. SAFETY

The safety and tolerability endpoints are:

- Unsolicited AEs during the 28 days following each vaccination
- Solicited local and systemic AEs (reactogenicity), collected daily from the day of vaccination for 7 days post-vaccination (day of vaccination and the subsequent 7 days). The investigator assessment of the solicited AEs is used in the safety analysis.
- Serious Adverse Events (SAEs) and Medically Attended Adverse Events (MAAEs) during the entire course of the study.

The safety and tolerability analysis will be performed on the FAS set. Specifically, the analysis for solicited adverse events will be done on those participants in the FAS set for whom reactogenicity assessments are available in the database (either via on-site assessments or via the diary pages of the CRF).

A ‘post any dose’ period (= regimen phase in section 2.1.1) will be added, that summarizes the safety after all administered doses of the vaccine. Each participant is counted only once. Whenever a participant has the same event after more than one dose, it will be counted only once (and in case of showing attributes, the worst corresponding attribute will be shown) in the post-any dose period. The denominator will be the number of participants that received the considered dose.

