### 4.1. Analysis of Adverse Events

Number and percentage of participants with at least one particular AE (unsolicited/solicited) will be tabulated. Unsolicited AEs will be summarized by System Organ Class and Preferred Term. Solicited AEs will be summarized by class (administration site, systemic) and preferred term.

For solicited AEs following tables will be provided: summary, by worst severity grade, grade 3 or above, related (systemic only), time to onset (in days) and duration (in days) for most frequent events and body temperature. Note: Duration is defined as number of days from the start of the event until resolution of the event. The time to first onset is defined as (date of first onset – reference date + 1). The reference date is the start date of the vaccination period.

For unsolicited AEs following tables will be provided: summary table (including SAE, fatal outcome, AESI and discontinuation), all events, most frequent, grade 3 or above, permanent stop of vaccine, related, SAE and AESI.

Listings and/or participant narratives will be provided as appropriate, for those participants who die, discontinue study vaccinations due to an AE, or experience a severe or serious AE.

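### AESIs are prospectively flagged only from local approval of Amendment 5, but the SAP tabulates them over everyone dosed, so absolute AESI rates may be understated

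*Protocol*

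**What the plan says.** **Start of reporting.** Footnote u of the protocol's Time and Events Schedule states "Applicable from the time of local approval of protocol amendment 5 onwards: AESIs (including potential AESIs) are to be reported to the sponsor". The amendment summary gives the date: "Amendment 5 (19 May 2021"). The Synopsis and Protocol 3.1, 9.4 and 12.3.1 also make TTS an AESI from local approval of that amendment, but then add: "All AESIs, including potential AESIs, will be reported to the sponsor from the moment of first vaccination until 6 months after the last vaccination". Protocol 9.1.4 likewise has AESIs recorded from the first vaccination. Protocol 9.1.5 sets the end: "AESIs are to be collected up to Visit 10 (6 months after the last vaccination").

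**Identification.** Under Protocol 12.3.4, AESIs and potential AESIs "must be reported using the AESI checkbox in the eCRF using the eCRF completion guidelines".

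**Analysis.** Protocol 11.6 states: "All safety analyses will be tabulated by vaccination group (active vaccine, placebo) and based on the FAS". SAP 4.1 plans an AESI table and a "summary table (including SAE, fatal outcome, AESI and discontinuation"). The only denominator rule in the SAP safety section is "The denominator will be the number of participants that received the considered dose". SAP 4.3 treats a participant with no reported event as a participant without one. AESIs are a secondary safety endpoint in Protocol 2.1 and SAP 1.1. The SAP's amendment history shows that they were added in version 1.2 (31 August 2023), after unblinding.

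**The concern.** The numerator and the denominator can cover different follow-up. The numerator depends on a flag that, under footnote u, came into use at each site no earlier than 19 May 2021. The denominator is everyone dosed, with no restriction by calendar date or approval date. Follow-up during which nobody was asked to tick the AESI box then enters the table as event-free.

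This matters because thrombosis with thrombocytopenia was made an AESI following events seen with another vaccine on the same Ad26 vector. Readers will look for an absolute rate or for a statement that no cases occurred among N vaccinees. Both look more reassuring than the data support if N includes follow-up without AESI ascertainment.

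**Working it through.** **1. Had dosing begun before Amendment 5?** The documents give no first-vaccination date. Amendment 3 (2 July 2020) added the COVID-19 appendix, which gives instructions for participants who have already had one or more vaccinations. Amendment 4 (10 March 2021) concerns participants enrolling or continuing. Both indicate dosing before 19 May 2021.

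**2. How much of a participant's window falls after 19 May 2021?** The window is 364 days to dose 4 plus about 183 days, or 547 days. The first-dose dates below are assumed.

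| Assumed first dose | Doses due before 19 May 2021 | Window after 19 May 2021 |
|---|---|---|
| 1 Jan 2020 | 4 | 43/547 = 8% |
| 1 Jul 2020 | 3 | 225/547 = 41% |
| 1 Jan 2021 | 2 | 409/547 = 75% |

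Later local approval lowers these shares. Being dosed before approval usually means partial coverage, not none. Under the planned accrual (12 months, half rate for the first 3) and an 18-month window, approval 12 months after first enrolment leaves 70% of the window covered on average, and nobody's window has closed. At 21 months the mean is 21%, and 14% of windows have closed.

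**3. What was captured before approval by other routes?** Protocol 9.4 has SAEs, MAAEs and events leading to discontinuation reported from first vaccination for the whole study, and unsolicited adverse events for 28 days after each dose. None of this depends on Amendment 5. The gaps are:
- non-serious, non-attended events more than 28 days after a dose. Protocol 1.1.2 describes TTS onset up to 42 days, and the AESI window runs to 6 months after the last dose;
- findings at a routine study visit, which Protocol 9.4 generally does not count as MAAEs;
- the AESI flag itself. An event recorded as an SAE or MAAE carries no checkbox, and the SAP has no term search that would find it.

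**4. Effect on a percentage.** Let f be the share of true AESIs arising before local approval, and c the share of those captured and classified anyway. The documents give neither. Then reported/true = 1 − f(1 − c).

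| f | c = 0 | c = 0.5 | c = 0.9 | c = 1 |
|---|---|---|---|---|
| 10% | 0.90 | 0.95 | 0.99 | 1 |
| 25% | 0.75 | 0.875 | 0.975 | 1 |
| 50% | 0.50 | 0.75 | 0.95 | 1 |
| 75% | 0.25 | 0.625 | 0.925 | 1 |

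**5. Effect on a zero-event statement.** The plan's own figures (Protocol 11.3, SAP 1.4) reproduce. With 1,900 vaccinees, the chance of at least one event at a rate of 1/1,000 is 1 − 0.999^1900 = 85%. The 95% upper bound with no events is 1 − 0.05^(1/1900) = 0.16%. If only part of the group is ascertained:
- 25% uncovered (n = 1,425): chance 76%, bound 0.21%.
- 50% uncovered (n = 950): chance 61%, bound 0.31% (0.32% by the rule of three, 3/950).

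This step treats uncovered follow-up as uncovered people and assumes no earlier capture, so it is an illustrative worst case for each share.

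**The case against.** The strongest reply is that the underlying events were largely recorded anyway. The Attachment 4 list includes pulmonary embolism, stroke, myocardial infarction and large-vessel thrombosis, which would ordinarily be serious or medically attended. The protocol draws no safety laboratory samples, so a low platelet count would usually surface through outside care and become an MAAE. This stands, and it is why c may be well above zero. It does not put those events into the AESI tables, because neither document says that earlier records are to be searched or reclassified.

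Second, the denominator sentence sits in the SAP paragraph on the period after any dose, and SAP Section 4 does not list AESIs among its endpoints. Mock tables are in the Data Presentation Specifications, and case review follows a committee charter; neither is available here. The AESI denominator is therefore better called unrestricted by default than expressly set. The FAS rule and SAP 4.3 still lead to the same table.

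A reader might also infer three stronger things, none of which the documents support:
- **That AESIs were collected only after approval, so the rate is wrong for everyone dosed earlier.** Several sections state reporting from first vaccination, and many earlier vaccinees would still have been inside the window at approval.
- **That the comparison of arms is biased.** Allocation is 1:1, blinded and stratified by site, so under-flagging before a site's approval should affect both arms alike. Safety is descriptive with no formal testing.
- **That TTS cases were missed.** The amendment summary for Amendment 5 reports none in the Ad26.Mos4.HIV studies, and Protocol 1.1.2, updated at Amendment 6, reports none with this vaccine.

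**Conclusion.** The concern holds for absolute AESI rates. The protocol passages on when AESI reporting starts need reconciling, and the SAP has no rule matching the AESI numerator to the follow-up in which AESIs were ascertained. Percentages and zero-event bounds may be understated for follow-up before each site's approval.

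The size cannot be derived, because first-dose dates, local approval dates and AESI counts are not in the documents. It ranges from nil, if every earlier event was captured and classified, to a shortfall equal to the share of events arising before approval, if none were. The share of the window in step 2 equals that shortfall only if nothing was captured and the hazard is constant over 547 days. Protocol 1.1.2 describes TTS onset as usually 1 to 4 weeks after vaccination, so constant hazard is doubtful for TTS. The practical effect is mainly on potential AESIs and on how a finding of no cases is worded.

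**What to change.** In SAP 4.1, derive AESIs and potential AESIs by applying the Attachment 4 preferred terms, plus thrombocytopenia terms, to all SAE, MAAE and unsolicited adverse event records from first vaccination, whether or not the checkbox was ticked. Use this as the main AESI table on the FAS.

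Show checkbox-reported AESIs separately, with the denominator or person-time limited to follow-up after the site's Amendment 5 approval. Base any zero-event bound on the matching denominator.

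Reconcile footnote u with the Synopsis and Protocol 3.1, 9.1.4, 9.4 and 12.3.1, so that the tables can state which follow-up they cover.

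The cost is one MedDRA query, the site approval dates and one extra table. The limitation is that earlier non-serious, non-attended events more than 28 days after a dose cannot be recovered; a footnote should say so.

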1. INTRODUCTION

In the development of the prophylactic VAC89220 HIV-1 vaccine, the sponsor is currently evaluating the following candidate components in clinical studies: Ad26.Mos4.HIV, (aluminum phosphate-adjuvanted) Clade C gp140 and Mosaic gp140. For details see Section 14.1.

For the most comprehensive nonclinical and clinical information regarding the VAC89220 HIV-1 vaccine, see the latest version of the Investigator's Brochures and Addenda for Ad26.Mos4.HIV, Clade C gp140 and Mosaic gp140.

The term "sponsor" used throughout this document refers to the entities listed in the Contact Information page(s), which will be provided as a separate document.

Other organizations, ie, the HIV Vaccine Trials Network (HVTN), Division of AIDS (DAIDS; a division of the National Institute of Allergy and Infectious Diseases [NIAID] which is part of the National Institutes of Health [NIH]) are also involved in this study and are referred to in this protocol as "partners".

1.1. Background

1.1.1. Background on the Disease and Treatment

Human immunodeficiency virus type 1 (HIV-1) is a retrovirus that, if left untreated, can progress to acquired immunodeficiency syndrome (AIDS), a condition in which the immune system is severely compromised, leading to life-threatening conditions. The main modes of transmission of HIV-1 in the world, although varying significantly by region, are heterosexual transmission, male-to-male transmission and intravenous drug use.³⁴ The global prevalence of HIV-1 in 2017 is estimated at 36.9 million (range: 31.1 to 43.9 million), which is an increase from previous years, mainly explained by broader access to life-saving antiretroviral therapy (ART) and a related longer life of HIV-infected individuals. Approximately 53% of all people living with HIV have access to ART. Despite an overall decline in HIV incidence and AIDS-related deaths, the number of new infections and the cost and morbidity associated with lifelong ART remain high. Worldwide, 1.8 million (range: 1.4 to 2.4 million) people became newly infected with HIV-1 in 2017.³⁵ HIV infection therefore continues to be a serious and potentially life-threatening condition of major global public health interest.

A number of specific approaches are being employed or evaluated to reduce the spread of HIV-1, but no single prevention method or approach utilized to date suggests that it will be able to stop the epidemic on its own. Several methods and interventions have proved highly efficacious in reducing the risk of, and protecting against, HIV infection, including male and female condoms, the use of ARV medicines as PrEP or as PEP, voluntary male medical circumcision, sexual activity change interventions to reduce the number of sexual partners, STI testing and treatment, the use of clean needles and syringes, opiate substitution therapy (eg, methadone) and the treatment of people living with HIV to reduce viral load and prevent onward transmission (treatment as prevention). Despite the availability of this widening array of efficacious HIV prevention tools

and methods in recent years, new infections among adults globally have not decreased sufficiently.^{33,36}

An effective, universal prophylactic HIV-1 vaccine could play a pivotal role in the so-called ‘HIV prevention toolbox’, where several HIV prevention methods will be necessary to play a significant role in controlling the spread of the infection.^{33,38}

Evidence for the potential to develop a prophylactic HIV-1 vaccine comes from study RV144 (sponsored by the United States Army Surgeon General, with vaccines manufactured by Sanofi Pasteur and VaxGen). The study was conducted in more than 16,000 healthy adult Thai participants who received recombinant canarypox vector encoding group-specific antigen (Gag), polymerase (Pol), and Env proteins of HIV-1 (ALVAC-HIV [vCP1521]) vaccine followed by a recombinant gp120 subunit vaccine (AIDSvax B/E). The vaccine afforded a modest (31%) reduction in the rate of HIV-1 acquisition.³⁰ In contrast to the Thai study, two Phase 3 studies of gp120 protein^{11,29} and three Phase 2b/3 studies using adenovirus serotype 5 (Ad5)-vectored Gag, Pol, and Negative Regulatory Factor (Nef) HIV-1 antigens^{7,16,17}, failed to demonstrate protection. Recently, study HVTN 702 or Uhambo, a Phase 2b/3 evaluating the efficacy of an investigational heterologous vaccine regimen (ie, ALVAC-HIV [vCP2438] + Bivalent Subtype C gp120/MF59) based on the regimen evaluated in the RV144 clinical study but adapted to HIV-1 Clade C which is most common in southern Africa, was stopped early because the vaccine was not efficacious.^{48,49}

A successful global HIV-1 vaccine will need to protect against the diverse strains and clades predominating in the target populations in different geographic regions. There is growing evidence that potent humoral responses with multiple effector functions combined with robust T cell responses will be necessary attributes of an effective HIV-1 vaccine. The HIV-1 genes expressed in the cytoplasm (eg, Gag and Pol) are primarily targeted by cytotoxic cellular immune responses, whereas the Env gp is a primary target of humoral responses.²⁶

